## 5.4. Safety

### 5.4.1. Analysis of safety planned in the protocol

Distribution of subjects by vaccinations will be summarized by vaccine group for the Exposed Set. The primary analysis will be performed on the Solicited / Unsolicited Safety Set.

#### 5.4.1.1. Within groups assessment

##### *Analysis of Solicited Adverse events*

All solicited AEs will be summarized according to defined severity grading scales, see [Table 6](#) and [Table 7](#).

**Table 6      Grading of Solicited Local Adverse Events (administration site events) for All Subjects**

Adverse Events	Grading of Severity			
	Grade 0	Mild	Moderate	Severe
Tenderness or discomfort to touch at injection site	None	Minor light reaction to touch	Cried or protested to touch	Cried when injected limb was moved
Hardness of skin at the injection site	0 mm	1 - 25 mm	26 - ≤50 mm	>50 mm
Swelling of skin at the injection site				
Redness at injection site				

**Table 7      Grading of Solicited Systemic Adverse Events for All Subjects**

Adverse Events	Grading of Severity			
	Grade 0	Mild	Moderate	Severe
Decreased eating	None	Eating less than normal for 1 - 2 feeds/ meals	Missed 1 or 2 feeds / meals	Missed more than 2 feeds/ meals
Increased sleepiness	None	Shows an increased drowsiness	Sleeps through feeds/ meals	Sleeps most of the time and it is hard to arouse him/her
Vomiting / throwing up	None	1-2 times in 24 hours	3 – 5 times in 24 hours	6 or more times in 24 hours or requires intravenous hydration
Loose stools / Diarrhea	Fewer than 2 loose stools in 24 hours	2 - 3 loose stools in 24 hours	4 - 5 loose stools in 24 hours	6 or more loose stools in 24 hours or requires intravenous hydration
Irritability	None	Requires more cuddling and is less playful than usual	More difficult to settle	Unable to console
Persistent / continuous crying	None	Crying less than 1 hour	Crying for 1 up to 3 hours	Crying for 3 or more hours
Rash 	0	1-50 lesions	51-150 lesions	>150 lesions
Parotid/salivary gland swelling 	None	Swelling without difficulty moving the jaw	Swelling with difficulty moving the jaw	Swelling with accompanying general symptoms
Fever 	<38.0°C (<100.4°F)	≥38.0 - 38.9°C (≥100.4 – 102.1°F)	≥39.0 - 39.9°C (≥102.2 – 103.9°F)	≥40.0°C (≥ 104.0°F)

Rash and parotid/salivary gland swelling will be recorded only after receiving the MMR and VV vaccines at 12 months of age at Visit 5 (Day 301). These specific systemic AEs, along with fever, will be recorded for 30 days following the MMR and VV vaccine administration.

Preferred locations for measuring temperature are the rectum for subjects <12 months of age and the axilla for subjects ≥12 months of age. Body temperature is to be recorded daily, ideally at the same time each day.

Frequencies and percentages of subjects (with 95% CI; [Frank, 2009; Clopper, 1934]) experiencing each AE will be presented for each symptom severity. Summary tables showing the occurrence of any local or systemic AE overall and at each time point will also be presented.

Post-vaccination solicited AE reported from Day 1 to Day 7 will be summarized for the interval Day 1-7 (and Day 1-3, Day 4-7 if needed) by maximal severity and by vaccine

group, excluding the 30-minute measurement, which will be summarized separately. For MMR and VV-specific solicited systemic AEs (parotid/salivary gland swelling, fever, rash) collected after Visit 5 (30 minutes through Day 30 post vaccination), the study period will be divided into the following intervals: 6 hours through Day 7, Day 8 through Day 30.

The severity of solicited local AEs (administration site events), including redness at injection site, swelling of skin at injection site, and hardness of skin at injection site will be summarized according to categories based on linear measurement: None (0 mm); Mild (1 mm to 25 mm); Moderate (26 mm to 50 mm); Severe (> 50mm).

Injection site tenderness and systemic reactions (except fever) occurring up to 7 days after each vaccination will be summarized according to “mild”, “moderate” or “severe”.

Fever, derived from measured body temperature ( $\geq 38.0^{\circ}\text{C}/100.4^{\circ}\text{F}$ ), will be summarized according to “Grade 0 (none)” ( $< 38.0^{\circ}\text{C}$ ), “mild” ( $\geq 38.0 - 38.9^{\circ}\text{C}$ ), “moderate” ( $\geq 39.0 - 39.9^{\circ}\text{C}$ ) and “severe” ( $\geq 40.0^{\circ}\text{C}$ ).

Each solicited local (administration site) and systemic AE will also be further summarized as “none” versus “any” (for fever the latter will be  $\geq 38.0^{\circ}\text{C}/100.4^{\circ}\text{F}$ ).

Use of antipyretics and analgesics will be summarized by type of use (prophylactic versus treatment) and percentage of subjects (with 95% CI) reporting use.

Body temperature will be summarized by  $0.5^{\circ}\text{C}$  increments from  $36.0^{\circ}\text{C}$  up to  $\geq 40^{\circ}\text{C}$  and will be broken down according by route of measurement, if applicable. Frequencies and percentages of subjects (with 95% CI) with temperatures  $\geq 38.0^{\circ}\text{C}$  and temperatures  $\geq 40.0^{\circ}\text{C}$  will also be presented.

Descriptive summary statistics will be provided for subgroups gender, race, and ethnic origin.

#### *Analysis of Unsolicited Adverse Events*

This analysis applies to all AEs occurring during the study, judged either as reasonable possibly related, or not reasonable possibly related to vaccination by the investigator, recorded in AE eCRF, with a start date on or after the date of first vaccination. All AEs starting prior to the first vaccination will only be listed. The original verbatim terms used by investigators to identify AEs in the eCRFs will be mapped to preferred terms using the MedDRA dictionary. The AEs will then be grouped by MedDRA preferred terms into frequency tables (with 95% CI; [Frank, 2009; Clopper, 1934]) according to system organ class.

All reported AEs, as well as AEs judged by the investigator as related to study vaccine, will be summarized according to system organ class and preferred term within system organ class. These summaries will be presented by vaccine group and by interval of study observation. When an AE occurs more than once for a subject, the maximal severity and strongest relationship to the vaccine group will be counted.

Serious adverse events, withdrawal due to AEs and AESIs will be described in detail.

Separate summaries will be produced for the following categories:

- Serious adverse events (SAE)
- Adverse events related to vaccine
- Adverse events of special interest (pIMDs, seizures, and/or arthritis)
- Adverse event leading to withdrawal with relationship to COVID-19
- Adverse events leading to a medically attended visit

These summaries will also be presented by the 0-6/0-12 months safety follow-up periods after the last study vaccination.

Data listings of all AEs will be provided by subject. In addition, AEs in the categories above will be provided as listed data.

Descriptive summary statistics will be provided for subgroups gender, race, ethnic origin and age group (6-8 weeks or  $\geq 8$  weeks), for the following parameters:

- Adverse events
- Adverse events related to vaccine
- Serious adverse events (SAE)
- Adverse events leading to a medically attended visit

In cases needed, a few specific AEs and SAEs (for example AESI) will be analysed statistically using Poisson regression, where the total number of days for which the subject was followed-up (excluding any pre-vaccination periods) will be used as an offset. The Poisson regression enables calculation of the risk ratio (RR) of a SAE or AESI, including 2-sided 95% CI, for each preferred term. Confidence intervals of RRs will not be adjusted for multiplicity. i.e., owing to the possible large number of comparisons it cannot be ruled out that potential safety signals occur by chance alone.

```
PROC GENMOD  DATA = <dataset name>;
  CLASS    ARMCD   SITEID;
  MODEL    AVAL = ARMCD SITEID / DIST = POISSON OFFSET = log(TIME) LINK
= LOG;
  ESTIMATE  'Beta A/B'  ARMCD  1  -1  / EXP;
RUN;
```

\*time: number of days the subject was followed-up;

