#### **5.4.1.2. Between groups assessment**

95% CIs for differences between vaccine groups will be provided according to Miettinen and Nurminen method [[Miettinen](#), 1985].

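### The optional Poisson rate ratio for AESIs and SAEs has no usable confidence interval when one arm has no event, and counting all follow-up pulls an acute post-dose excess towards 1

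*SAP*

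**What the plan says.** SAP 5.4.1.1 (Analysis of Unsolicited Adverse Events) makes the model conditional: "In cases needed, a few specific AEs and SAEs (for example AESI) will be analysed statistically using Poisson regression". The sentence goes on to set the offset: "where the total number of days for which the subject was followed-up (excluding any pre-vaccination periods) will be used as an offset". The model line is "AVAL = ARMCD SITEID / DIST = POISSON OFFSET = log(TIME) LINK", so arm and site are fixed effects, and an ESTIMATE statement with EXP returns the arm contrast. On the output, the SAP says: "The Poisson regression enables calculation of the risk ratio (RR) of a SAE or AESI, including 2-sided 95% CI, for each preferred term". It adds "Confidence intervals of RRs will not be adjusted for multiplicity". It gives no post-dose window, no trigger for using the model, no rule for an arm without events, and no exact or profile-likelihood option.

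Two other provisions matter.

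- SAP 5.4.1.2 states: "95% CIs for differences between vaccine groups will be provided according to Miettinen and Nurminen method". It names neither events nor intervals.
- Of the AE tables, SAP 5.4.1.1 says: "These summaries will be presented by vaccine group and by interval of study observation". Protocol 9.3 supplies intervals for SAEs, AESIs, medically attended AEs and AEs leading to withdrawal: Days 1 to 30 after each dose, then Day 31 to the next dose or study end.

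Protocol 9.6.2 marks between-group safety assessment as not applicable, so both between-group methods come from the SAP.

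**The concern.** AESIs and many SAE terms are rare, and the placebo group has only 400 infants. A safety signal would first appear as a few events, mostly or all in the MenB+PCV arm. A rate ratio should remain computable in that setting, and the coded one does not.

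The second issue is the period counted. Protocol 1.3.1 lists seizure, including febrile seizure, as a potential risk of rMenB+OMV NZ. It describes seizures soon after immunization as mostly fever-related and puts the peak of febrile convulsions at 18 months of age. Day 481 is 180 days after the 12-month dose, so about 18 months of age, and some infants are followed to Day 661. A whole-period count therefore mixes a short post-dose risk with background events from an age when they are common. A ratio near 1 could be read as reassurance when it mainly reflects background.

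**Working it through.** The documents give no event rate, event count or power for this comparison, so there is no planned figure to reproduce. Inputs from the documents are 800 and 400 infants (2:1), doses on Days 1, 61, 121 and 301, and follow-up to Day 481 or 661. Risks and true rate ratios below are assumptions.

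**1. Limits from the code.** The SAP does not use the word Wald. It follows from ESTIMATE with EXP, which exponentiates the log ratio plus or minus 1.96 standard errors.

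**2. Empty arm.** With no control event the maximum-likelihood log ratio is infinite. A fit at 6 v 0 (no site term) stopped at a log ratio of about 21 with a standard error of about 13,000, which gives an interval of 0 to infinity. The same happened at 2, 4, 8 and 10 v 0 and at 0 v 3.

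**3. How often.** P(no event in 400 controls) = (1 − p)^400:

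- p = 0.1%: 67%
- p = 0.25%: 37%
- p = 0.5%: 13%
- p = 1%: 2%

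**4. Alternative limits.** With n v 0 events and 2:1 exposure, the lower limit of the ratio is p_L / [2(1 − p_L)]. For exact conditional limits p_L = 0.025^(1/n). For profile likelihood p_L = exp(−3.84/(2n)). At 6 v 0 the exact p_L is 0.541, so the limit is 0.541/(2 × 0.459) = 0.59. The profile p_L is 0.726, so the limit is 0.726/(2 × 0.274) = 1.33. The upper limit is infinite throughout. The last column is (2/3)^n, the chance that all n events fall in the MenB+PCV arm when there is no effect.

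| Events | Wald | Profile lower | Exact lower | (2/3)^n |
|---|---|---|---|---|
| 4 v 0 | 0 to ∞ | 0.81 | 0.33 | 20% |
| 6 v 0 | 0 to ∞ | 1.33 | 0.59 | 9% |
| 8 v 0 | 0 to ∞ | 1.84 | 0.85 | 4% |
| 10 v 0 | 0 to ∞ | 2.36 | 1.12 | 1.7% |

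**5. Dilution.** With constant background, whole-period ratio = f × RR + (1 − f), where f = window days / total days. Four 30-day windows are 120 days. For RR = 3:

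- 480 days: f = 0.25, ratio = 0.75 + 0.75 = 1.50
- 660 days: f = 0.182, ratio = 0.545 + 0.818 = 1.36

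For four 7-day windows (28 days) the ratios are 1.12 and 1.08. If no events occur outside the window there is no dilution.

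**6. Both changes or one.** Simulation (100,000 runs per row, 661 days, Day 1 to 30 windows), chance that the lower limit exceeds 1:

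| Background, acute RR | Whole, Wald | Whole, exact | Window, Wald | Window, exact |
|---|---|---|---|---|
| 1%, 10 | 37% | 40% | 16% | 69% |
| 2%, 5 | 24% | 22% | 19% | 49% |
| 1%, 5 | 6% | 10% | 0.1% | 10% |
| 0.5%, 10 | 3% | 14% | 0.1% | 14% |

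In the first row, windowing leaves no control event in 48% of trials, which is why windowing with Wald limits does worse than no change. With 7-day windows, 1% background and RR 10, every method stays below 5%.

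**7. Site term.** In a 40-site fit with 4 to 8 events, most sites had none, yet the arm ratio and its standard error were the same with and without SITEID.

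**The case against.** The strongest reply is that this model carries little weight. It is optional, SAP section 6 calls the safety endpoints descriptive, and SAP 5.4.1.2 plans difference intervals that survive an empty arm. The Miettinen-Nurminen interval is 0.75% (−0.20% to 1.63%) at 6 v 0 and 1.00% (0.05% to 1.96%) at 8 v 0. It excludes no difference at 8 v 0, whereas the exact ratio limit does so only at 10 v 0. Background outside the window adds noise to a difference but does not shrink the absolute excess. Day 1 to 30 counts by group are also planned, and the third primary safety endpoint covers SAEs and AESIs in the 30 days after each dose. Whole follow-up is itself a stated endpoint period and suits events without a short risk window, such as arthritis.

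All of that stands, and it limits the point. It does not supply a stated between-group interval for AESIs or SAEs within a post-dose window, because SAP 5.4.1.2 names no events or intervals. Nor does it make the coded ratio computable.

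A reader might infer four stronger things that the documents do not support:

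- That this regression is the plan's means of judging AESIs and SAEs. It is the only regression for AEs, but not the only between-group comparison.
- That the offset causes the dilution. With equal follow-up it cancels from the ratio. The dilution comes from counting background events outside the window.
- That sites without events break the model. They do not; an empty arm does.
- That 7-day windows would add detection. With the 1% background in step 6 they do not.

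**Conclusion.** The point holds in a limited form. As coded, the ratio fails whenever an arm is empty, which is a realistic outcome for rare terms (13% to 37% at control risks of 0.5% to 0.25%). For events with background incidence, it also understates an acute excess (3 becomes 1.5 or 1.36 with 30-day windows). The failure follows from the code and needs no assumption. Its frequency, the dilution and the simulated gains rest on assumed risks and rate ratios, constant background and full enrolment of 800 and 400. The gain from the fix is not uniform: at 0.5% background and RR 10, exact limits over the whole period do as well as exact limits in the window (14% each). Part of the gap is covered elsewhere in the SAP and protocol, so this is a worthwhile correction to an optional analysis. It does not show that the safety evaluation as a whole is unsound.

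**What to change.** Where the SAP 5.4.1.1 ratio is produced:

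- **Limits.** Replace the Wald limits with exact conditional Poisson or profile-likelihood limits, and name the choice in advance. Both keep a finite lower limit with no control event. Exact limits are conservative. Profile limits are liberal here: at 6 v 0 the lower limit is 1.33, although chance alone puts all six events in the larger arm 9% of the time. Exact is the safer default.
- **Window.** Report the ratio, together with the Miettinen-Nurminen difference, for Days 1 to 30 after each dose as defined in Protocol 9.3, with days observed in the window as the offset. Keep the total follow-up result alongside it.
- **Site.** Keep SITEID.

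Make the first two changes together, for the reason in step 6. The cost is a SAP code edit and a few extra table rows, with no new data. The price of exact limits is that, with no control event, the lower limit first exceeds 1 at 10 v 0, and the upper limit stays infinite.

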7.1.6.1. Febrile seizures

Seizures are defined according to the Brighton Collaboration Working Group (BCWG) case definition of generalized convulsive seizure as an adverse event following immunization [[Bonhoeffer](#), 2004].

The list of Preferred Terms (PTs) corresponding to the diagnosis of seizure, are those included in the Medical Dictionary for Regulatory Activities (MedDRA) Standard MedDRA Query (SMQ) Narrow “Generalized convulsive seizures following immunization”.

For any new diagnosis of generalized convulsive seizure (including febrile seizure), irrespective of seriousness, the investigator (or designate) must complete, an electronic Expedited Adverse Events Report and an ad-hoc eCRF page on seizures to further characterize this AESI.

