7.1.6.2. Arthritis

Cases of arthritis are defined according to the following ad-hoc definition:

- Presence of a physical exam findings of swelling, redness, heat, or limitation in range of motion and/or
- Presence of a diagnostic imaging studies interpreted by a health care provider as demonstrating evidence of joint inflammation and/or arthrocentesis results evidencing inflammation.

Due to the heterogeneity of the presentation of arthritis which can be either acute or chronic, the threshold of duration of symptoms of 6 weeks is to be considered.

The list of PTs corresponding to the diagnosis of arthritis, are those included in the MedDRA SMQ Narrow “Arthritis”. For any new diagnosis of arthritis (serious or non-serious) in a study subject, the investigator (or designate) must complete, an electronic Expedited Adverse Events Report and an ad-hoc eCRF page on arthritis to further characterize this AESI.

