
 - Churg-Strauss syndrome (allergic granulomatous angiitis or eosinophilic granulomatosis with polyangiitis), - Buerger's disease (thromboangiitis obliterans), - Necrotizing vasculitis 		
 • Ocular autoimmune diseases including: 
 - Autoimmune uveitis - Autoimmune retinitis. • Autoimmune myocarditis. • Sarcoidosis. • Stevens-Johnson syndrome. • Sjögren's syndrome.

 - (cutaneous or systemic), - anti-neutrophil cytoplasmic antibody (ANCA) positive vasculitis (type unspecified), - Henoch-Schonlein purpura (IgA vasculitis), - Behcet's syndrome, - Leukocytoclastic vasculitis. 		
 • Alopecia areata. • Idiopathic pulmonary fibrosis. • Goodpasture syndrome. • Raynaud's phenomenon.
Liver disorders	Gastrointestinal disorders	Endocrine disorders

 • Autoimmune hepatitis. • Primary biliary cirrhosis. • Primary sclerosing cholangitis. • Autoimmune cholangitis. 	
 • Inflammatory Bowel disease, including: 
 - Crohn's disease, - Ulcerative colitis, - Microscopic colitis, - Ulcerative proctitis. • Celiac disease. • Autoimmune pancreatitis. 	
 • Autoimmune thyroiditis (Hashimoto thyroiditis). • Grave's or Basedow's disease. • Diabetes mellitus type I. • Addison's disease. • Polyglandular autoimmune syndrome. • Autoimmune hypophysitis.

When there is enough evidence to make any of the above diagnoses, the AE must be reported as a pIMD. Symptoms, signs or conditions which might (or might not) represent the above diagnoses, should be recorded and reported as AEs but not as pIMDs until the final or definitive diagnosis has been determined, and alternative diagnoses have been eliminated or shown to be less likely.

In order to facilitate the documentation of pIMDs in the eCRF, a pIMD standard questionnaire and a list of MedDRA preferred terms (PTs) and PT codes corresponding to the above diagnoses will be available to investigators at study start.

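### The SAP's optional Poisson risk ratio for AESIs is specified per preferred term rather than per AESI, so when it is used it is less precise and more often has an empty arm

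*SAP*

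**What the plan says.** **The model.** SAP 5.4.1.1 (Analysis of Unsolicited Adverse Events) introduces it conditionally: "In cases needed, a few specific AEs and SAEs (for example AESI) will be analysed statistically using Poisson regression". Log follow-up time is the offset, and group and site are the factors. The stated output is the "risk ratio (RR) of a SAE or AESI, including 2-sided 95% CI, for each preferred term". On multiplicity: "Confidence intervals of RRs will not be adjusted for multiplicity".

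**What an AESI is.** The protocol defines two of the three AESI types by a list of terms.
- Seizure (7.1.6.1): "The list of Preferred Terms (PTs) corresponding to the diagnosis of seizure, are those included in the Medical Dictionary for Regulatory Activities", through a narrow SMQ for generalized convulsive seizures after immunization.
- Arthritis (7.1.6.2): "The list of PTs corresponding to the diagnosis of arthritis, are those included in the MedDRA SMQ Narrow".
- pIMDs (7.1.6.3) are a long table of diagnoses, supported by "a list of MedDRA preferred terms (PTs) and PT codes corresponding to the above diagnoses".

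**What else is planned.**
- The primary safety endpoint counts subjects with AESIs from Day 1 to study end (SAP section 3).
- SAP 5.4.1.1 orders a separate summary of "Adverse events of special interest (pIMDs, seizures, and/or arthritis", with listings and a detailed description.
- SAP 5.4.1.2 promises Miettinen-Nurminen 95% intervals for group differences, without saying for which events or at what level.
- SAP section 6 makes the safety endpoints descriptive.

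**The concern.** The unit of the risk ratio does not match the unit in which the plan defines the outcome. Seizure cases coded to different terms of the SMQ would be analysed as separate, rarer outcomes, each with its own wide interval. The same holds for arthritis. Sparse terms also make it more likely that one arm has no event. A maximum-likelihood Poisson ratio then has no finite estimate, and the site factor in the SAP's code thins the data further.

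Seizure, including febrile seizure, is listed in protocol 1.3.1 as an important potential risk of the MenB vaccine, to be monitored through AESI collection. If the model is needed at all, this is a likely place for it, and it should then address the outcome as the protocol defines it.

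**Working it through.** The documents give no AESI rate, target ratio or expected count for safety, so there is no planned figure to reproduce. What follows is an illustration.

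**Inputs from the documents.** 800 and 400 infants (protocol 4.1 and Table 1); two-sided 95% interval without adjustment, per preferred term (SAP 5.4.1.1).

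**Assumptions, not in the documents.** Control risk p, true ratio RR, share s of the events that falls in the term analysed, equal follow-up, no site term.

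**Step 1: the Poisson ratio, pooled and by term.** Let a ~ Poisson(800·p·RR·s) and b ~ Poisson(400·p·s). The Wald interval is log[(a/800)/(b/400)] ± 1.96·√(1/a + 1/b). An excess is shown if the lower limit is above 0. The chance of an empty arm is 1 − (1 − e^(−λ₁))(1 − e^(−λ₂)), where λ₁ and λ₂ are the expected counts. Summing over all counts:

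| p, RR | Share s | Expected events | Lower limit of RR above 1 | An arm empty |
|---|---|---|---|---|
| 1%, 3 | 100% (pooled) | 24 v 4 | 52.5% | 1.8% |
| | 90% | 21.6 v 3.6 | 44.7% | 2.7% |
| | 60% | 14.4 v 2.4 | 14.8% | 9% |
| | 25% | 6 v 1 | 0.02% | 37% |
| | 15% | 3.6 v 0.6 | <0.01% | 56% |
| 0.5%, 4 | 100% (pooled) | 16 v 2 | 26.4% | 14% |
| | 60% | 9.6 v 1.2 | 1.5% | 30% |
| | 25% | 4 v 0.5 | <0.01% | 61% |
| | 15% | 2.4 v 0.3 | <0.01% | 76% |

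**Step 2: a different test and a different split.** Given T events in total and no effect, the MenB+PCV count is Binomial(T, 2/3). A term with no placebo case needs at least 10 events, all in MenB+PCV, before the exact lower limit passes 1: (2/3)^10 = 0.0173, while (2/3)^9 = 0.0260. Twelve against none gives one-sided p = 0.0077; the same events as four terms of three against none give p = 0.296 each. With events spread evenly over four terms, at 1% and RR 3, the chance is 54.3% pooled, 3.2% for one term and 12.3% for at least one of the four.

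**Step 3: where pooling does not help much.** At a control risk of 0.25%, the exact pooled chance is itself only 0.3% (RR 2) to 11.8% (RR 4).

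**Step 4: the difference interval, if applied to the pooled AESI.** With binomial counts, the Miettinen-Nurminen lower limit exceeds 0 when (a/800 − b/400)/√[p̄(1 − p̄)(1/800 + 1/400)·1200/1199] > 1.96, where p̄ = (a + b)/1200. That happens in about 64% of trials (1%, RR 3) and 57% (0.5%, RR 4). The interval exists with an empty arm: 12/800 against 0/400 gives a difference of 1.5% (0.54% to 2.60%).

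**The case against.** A reader might infer that a seizure or arthritis signal would be hidden from the trial. The documents do not support that. Subjects with AESIs are counted as an endpoint and summarised as a category, and nothing restricts the difference intervals of SAP 5.4.1.2 to preferred terms. By Step 4, those intervals, if applied to the pooled AESI, would show an excess more often than the pooled Wald ratio (64% against 52.5%, and 57% against 26.4%). This part of the objection stands.

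It also stands that the Poisson model is optional, that safety is descriptive, and that no conclusion depends on the ratio. The rates and the split over terms are invented: if one term holds 90% of events, most of the loss disappears. A ratio for any pIMD would combine unrelated diagnoses, so pooling has little to offer there.

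Two further arguments carry less weight. The SAP sentence says what the regression makes possible, its code uses a generic outcome variable, and table detail is left to a separate output specification, so a category-level run is not excluded. But the only level the SAP names is the preferred term. And SAP 5.4.1.2 cannot be relied on as it stands: it names neither the events nor the level, and it does not use the follow-up time that the Poisson model takes as its offset, although planned follow-up is 6 or 12 months.

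**Conclusion.** The point holds for the risk-ratio analysis only. The stated unit is finer than the outcome the protocol defines for seizure and arthritis, and no risk ratio is specified at the AESI level. When the model is used, splitting costs precision and makes an empty arm more likely. It cannot add information about the group.

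The size depends on assumptions. At 1% control risk and RR 3, the chance that the interval lies above 1 falls from about 52% pooled to 15% for a term with 60% of events, but only to 45% for a term with 90%. At very low rates neither version is informative. Since the category summaries and the promised difference intervals remain, the trial's ability to see an excess is not lost. Severity: minor.

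**What to change.** In SAP 5.4.1.1, replace the per-preferred-term specification by a risk ratio for each AESI category, counting each infant once per category: seizure as all terms of the SMQ named in protocol 7.1.6.1, and arthritis as all terms of the SMQ named in 7.1.6.2. Keep the preferred-term ratios as supportive detail. Label any ratio for pIMDs as a whole as descriptive only.

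In SAP 5.4.1.2, state that the Miettinen-Nurminen differences are also given for these categories. That keeps an interval when one arm has no event.

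The cost is SAP wording, one grouping flag in the adverse-event dataset and one more table. No new data are needed, and the conduct of the trial does not change.
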